# 4.2.3.2 Description of the trial procedures

# 4.2.3.2.1 Collection of medical history, demographic and anthropometric data

Medical history includes the previous diseases, concomitant chronic conditions, hereditary issues, social habits (smoking, alcohol or drug abuse), allergological anamnesis, previous surgeries or traumas, occupational history, permanent or periodic drug therapy. Regarding the present condition: date and time of the first signs manifestation, diagnostic and treatment procedures by the screening, their efficacy. A contraception method used by the patient; by signing the Informed Consent Form, the patient agrees to use one of the recommended contraception methods (by the protocol) during the trial and 1 month after the trial completion.

Primary documents must contain data on the sex, age, race, and ethnicity of the patient. A height meter is used to measure the patient's height in centimeters, the weighing scales—body weight in kilograms.

The anthropometric examinations will be conducted in accordance with the Health Risk Monitoring (EHRM) Recommendation for indicators, international collaboration, protocol and manual of operations for chronic disease risk factor surveys, 2002 (17).

Height should be measured in all the patients (the causes which make the height measurement impossible include hair-style peculiarities (e.g., mohawk), patient's refusal to take off a headwear (e.g., turban), patient's incapacity to stand, exceedance of the height meter's scale). The height meter is a vertically positioned panel with a centimeter division with a sliding horizontal ruler. A standard error must not exceed 2 mm. The patient will be asked to take off his/her shoes, thick clothes, hairpins, or other hair accessories. The patient must touch a vertical panel with his/her hindhead, back, buttocks, calves, and heels (the toes are stuck together). Upper boundary of the external ear canal must be at the same level with lower boundary of the orbital cavity (the jugal bone). The patient will be asked to look forward. If the patient's height exceeds that of the Investigator, the latter should use a platform. A height meter's ruler is put on the patient's head, the scale's divisions are counted. The height must be recorded while the patient is still standing under the ruler. An error must not exceed 0.5 cm.

The patient's weight must be measured in the morning in the fasting condition, after urination and defecation, in the underwear (with further subtraction of an average underwear weight). The weighing scales must be horizontally positioned on a solid ground. An error must not exceed 0.2 kg. The patient should stand in the center of the weighing scales on the both legs. If the weight measurement is impossible, the Investigator should not record any values based on the patient's claims.

Confidential

# 4.2.3.2.2 Physical examination and vital signs evaluation

Physical examination will be conducted according to the general rules of the propedeutics of internal diseases: general visual examination, inspection of the mucous membranes, including pharyngoscopy, lymph nodes palpation, evaluation of bones and muscles, palpation, percussion and auscultation of the main organ systems (cardiovascular, respiratory, gastrointestinal, urinary systems) will be conducted sequentially.

Vital signs (HR, BR, BP, body temperature) will be evaluated before the physical examination at rest (after 15 minutes of rest, not earlier than 1 hour after smoking or 2 hours after meal). Heart rate (HR) will be measured during the heart auscultation in parallel with a pulse rate determination on the radial artery (or carotid artery in case the radial artery pulse is weak) for 1 minute in a sitting position; in case of a pulse deficiency, the both parameters should be recorded: HR and pulse rate. Breathing rate (BR) will be measured for 1 minute at rest, in a sitting position, observing breathing movements of the thorax and abdominal wall without drawing the patient's attention.

Blood pressure (BP) will be measured on the brachial artery, in a sitting position, by Korotkoff method, using a certified sphygmomanometer or tonometer with a cuff adjusted for the patient's shoulder in length and width according to the recommendations for measurement (RMOAG/VNOK, 2010). The cuff's size should correspond to the arm's size: a cuff rubber part to be inflated should cover not less than 80% of the arm circumference; a cuff 12–13 cm in length and 30–35 cm in width (medium size) should be used for the adults; although, the bigger and smaller cuffs might be required for bigger and smaller arms, respectively. Before the measurement start, a mercury column or a tonometer needle must be in a zero position. To measure BP on every arm not less than 2 measurements with a 1-minute interval are required; in case of BP difference  $\geq$ 5 mm Hg, an additional measurement should be made; the lowest result based on the 3 measurement should be recorded as a final one.

Measurement procedure:

- Pump up the air into the cuff fast to the pressure level 20 mm Hg exceeding a common systolic BP (by the pulse disappearance).
- An error must not exceed 2 mm Hg.
- Reduce the pressure in the cuff at a rate of 2 mm Hg per second.
- A pressure level when the 1st tone appears corresponds to a systolic BP (phase 1 of Korotkoff sounds).
- A pressure level when the tones disappear corresponds to a diastolic BP (phase 5 of Korotkoff sounds); in children, adolescents, and young people after physical exertion, in pregnant women, as well as in some disorders in adults when phase 5 cannot be determined, a healthcare practitioner should try to determine phase 4 by significant tones weakening.

- If the tones are very weak, the patient should raise his/her hand and make several compressions by hand, after which the measurement should be repeated without a strong compression on the artery by a phonendoscope membrane.
- BP should be measured on both hands at initial examination only; further measurements must be performed at the hand with higher values.

Body temperature must be measured by the same thermometer type (mercuric or electronic) and method (axillary temperature) throughout the trial.

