#### 5 Selection and exclusion of the subjects

#### 5.1 Inclusion criteria

The patients who meet all the inclusion criteria listed below will be included in the trial:

- 1. The Informed Consent Form voluntarily signed by the patient.
- 2. Men and women at the age of 18 to 45 years old, inclusively.
- 3. A diagnosis of acute, uncomplicated, inflammatory and infectious condition of the pharynx associated with the inflammation and pain in the throat.
- 4. Manifestation of the first signs of acute, uncomplicated, inflammatory and infectious condition of the throat (pharyngitis and/or tonsillitis) not more than 48 hours before the inclusion.
- 5. A baseline total sum of TSS (Tonsillopharyngitis Severity Score) points  $\geq$ 5.
- 6. Body temperature measured in the axillary cavity is less than 37.5 °C.
- 7. Women with childbearing potential should demonstrate a negative pregnancy test result at screening (except for the women after surgical sterilization or menopause for more than 2 years) and use the established contraception methods for at least 3 months before the initiation of the trial therapy and 1 month after completion of the trial.
- 8. Men should use adequate contraception during the trial, since signing of the Informed Consent Form and till the trial completion, and for 30 days after the trial completion.
- 9. Ability to understand the presented information on the clinical trial, readiness to comply with the protocol, ability to use the study drugs by oneself and evaluate the symptoms according to VAS (visual analogue scale) or other questionnaires according to the protocol.

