  - a. Severe (IV acc. to Canadian Cardiovascular Society) or unstable angina;
  - b. Decompensated chronic heart failure (NYHA stage IV);
  - c. Myocardial infarction for the last 6 months;
  - d. uncontrolled arterial hypertension (BP more than 180/115 mm Hg).

- 24. Pregnant and/or breastfeeding women.
- 25. Participation in other clinical trials at the screening visit or for 30 days before the screening visit.
- 26. Surgical intervention for 30 days before the screening visit or planned surgical treatment during the trial (sooner than a follow-up visit is completed), including diagnostic procedures or hospital stay.
- 27. Known or suspected narcotic/alcohol abuse.
- 28. A suspected low compliance or incapability of the patient to perform the procedures and comply with restrictions according to the trial protocol (e.g., due to mental disorders).
- 29. Any cardiovascular, renal, hepatic, gastrointestinal, endocrine, or nervous disorders, or any other conditions/diseases which, in the Investigator's opinion, might inflict harm to the patient's health.

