# 9.1.4 Safety parameters analysis

A descriptive part of the safety analysis will include an evaluation of incidences and two-sided CI 95% for the following parameters in every trial group:

- AEs: the incidence in total and for separate categories (according to MedDRA), for the trial and by groups;
- SAEs: the incidence in total and for separate categories (according to MedDRA), for the trial and by groups;
- Incidence of clinically significant changes of the physical examination results by visits and groups;
- Incidence of clinically significant changes of the laboratory results by visits and groups;
- Incidence of clinically significant changes of the vital signs (body temperature, BP, pulse rate, HR) by visits and groups;
- Incidence of clinically significant changes of the ECG parameters by visits and groups;
- Global tolerance evaluation during the trial by the Investigator and patient;

The Fisher's exact test will be used to compare incidences between the groups, and chi-square will be used to compare the global therapy tolerability by the Investigator and patient. The McNemar's test will be used to evaluate for the dynamic changes during the trial (before–after) for all the repeatedly evaluated incidences in every group.

In addition to the incidence, all the quantitative safety parameters will be presented in a table form (laboratory data, vital signs, ECG) by visits and groups. The difference will be evaluated using 2-way-ANOVA (group and visit numbers will serve as the relevant factors). The post-hoc criteria will be used in case of significant difference.

Safety analysis will be performed on the safety population.

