# 4.1.5 Analysis of laboratory and functional tests results

A between group comparison of the vital signs changes (systolic blood pressure, diastolic blood pressure, breathing rate, heart rate, body temperature) revealed at every visit (Visits 1, 2, 3) as well as laboratory results and ECG changes incidence obtained at Visit 1 and Visits 2–3 is envisaged. In addition, significance of the changes will be evaluated for all repeatedly measured parameters.

The following laboratory parameters will be reviewed:

- Hematology
  - o Hemoglobin
  - o RBC
  - o ESR
  - o WBC
  - o Neutrophils
    - Juvenile
    - Stab
    - Segmented
  - o Eosinophils
  - o Basophils
  - o Monocytes
  - o Lymphocytes
- Biochemistry
  - o Total protein
  - o AST
  - o ALT
  - o Total bilirubin

ANOVA methods will be used to reveal a simultaneous influence of a group and time factors on the quantitative parameters.

The cross tables analysis will be used to reveal a correlation between the qualitative parameters (chi-squared test).

For the quantitative parameters, a comparison will be made by Student's t-test for the independent samples (in case of confirmation of hypothesis on normal variables distribution) or Mann–Whitney test (in case of rejection of hypothesis on normal variables distribution); for the qualitative parameters—using Fisher's exact test.

To evaluate significance of the intragroup changes during the trial for repeatedly measured parameters, the paired Student's t-test (in case of confirmation of hypothesis on normal variables distribution) or paired Wilcoxon signed-rank test (in case of rejection of hypothesis on normal variables distribution) will be used; for the qualitative parameters McNemar's test will be used.

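### When two blood pressure readings differ by 5 mm Hg or more, the lowest of three is recorded, which understates BP levels and adds avoidable noise to the vital-sign analyses

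*Protocol*

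**What the plan says.** **How BP is measured.** Protocol Section 4.2.3.2.2 sets the number of readings: "To measure BP on every arm not less than 2 measurements with a 1-minute interval are required". If the difference is at or above the stated limit of "5 mm Hg, an additional measurement should be made", and "the lowest result based on the 3 measurement should be recorded as a final one". Nothing is said about the value to record when the first two readings differ by less than 5 mm Hg. On the choice of limb, the same section adds: "BP should be measured on both hands at initial examination only; further measurements must be performed at the hand with higher values". No other part of the Protocol or SAP substitutes a mean or median.

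**How BP is used.**
- It is a listed safety parameter (Protocol Sections 4.1.2 and 8.1).
- Protocol Section 9.1.4 tabulates "Incidence of clinically significant changes of the vital signs (body temperature, BP, pulse rate, HR) by visits and groups" and analyses quantitative safety parameters by two-way ANOVA on group and visit.
- SAP Section 4.1.5 plans "A between group comparison of the vital signs changes", and SAP Table 7 summarises systolic and diastolic values at Visits 1, 2 and 3.
- Visit 1 BP is also the value available for non-inclusion criterion 23d: "uncontrolled arterial hypertension (BP more than 180/115 mm Hg" (Protocol Section 5.2).

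**The concern.** The lowest of three readings is a downward-biased estimate of a patient's BP. Here it is used only when the first two readings are far apart, so the understatement falls on the most variable measurements. When the readings agree, a site may enter the first, the last, the lower or the mean. Recorded BP can therefore mix different estimators across visits and sites.

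Two things are at stake. The absolute levels in the safety tables will be too low. The recorded value will also be noisier than the readings already taken allow, and that noise carries into the analyses of change, where it produces more apparent changes by chance.

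**Working it through.** The documents state no figure for BP variability, so there is nothing of the plan's own to reproduce. The size was found by simulating the recording rule.

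**Inputs from Protocol Section 4.2.3.2.2:** two readings, a third if they differ by 5 mm Hg or more, and the minimum of three recorded in that case.

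**Assumptions:**
- Within-visit SD of a single reading is 2 to 8 mm Hg.
- Readings are independent and normal around the true value, with no trend across repeats.
- The mean of two is recorded when no third reading is triggered.

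**Step 1. How often a third reading is triggered.** The difference of two readings has SD equal to √2 × SD, so P(trigger) = 2[1 − Φ(5 / (√2 × SD))]. At SD 5 this is 2[1 − Φ(0.707)] = 0.48. The simulation (2,000,000 sets of three readings per SD) agrees.

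**Step 2. Size of the understatement.** Bias over all measurements = P(trigger) × bias when triggered, because the mean of two carries no bias. At SD 5: 0.480 × (−5.45) = −2.6 mm Hg.

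| Assumed SD (mm Hg) | Third reading triggered | Bias when triggered (mm Hg) | Bias over all measurements, one limb (mm Hg) |
|---|---|---|---|
| 2 | 8% | −3.2 | −0.2 |
| 3 | 24% | −3.9 | −0.9 |
| 4 | 38% | −4.7 | −1.8 |
| 5 | 48% | −5.5 | −2.6 |
| 6 | 56% | −6.3 | −3.5 |
| 8 | 66% | −7.9 | −5.2 |

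If the mean of three is recorded after the trigger, the bias is 0.0 at every SD.

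**Step 3. Added noise.** The within-visit variance of the recorded value, relative to recording the mean, is 1.4 at SD 2, 1.75 at SD 3 and about 1.9 at SD 4 to 8. At SD 5 the recorded value has SD 4.5, so measurement error in a change between two visits has SD √2 × 4.5 = 6.4 mm Hg. With the mean it is 6.4 / √1.92 = 4.6.

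**Step 4. Effect on change.** The same rule applies at both visits, so the expected bias in change on one limb is 0.0. A true rise of 8 mm Hg is recorded as 8.0 on average at every SD. The share of such patients showing a recorded rise of 10 mm Hg or more (an illustrative cut; the documents set none) is larger under the written rule than under the mean: 35% against 30% at SD 4, 38% against 33% at SD 5, and 42% against 39% at SD 8. Extra noise pushes more values past a cut that lies above the true change.

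**Step 5. Entry limit.** Take a true systolic BP of 184 on both limbs. On one limb the chance of a recorded value of 180 or below is 27, 38, 46 and 57% at SD 4, 5, 6 and 8, against 6, 11, 15 and 21% with the mean. Both limbs are measured at the initial examination. If the higher limb's value counts, which is an assumption, both limbs must read low and the one-limb chance is squared. At SD 4, 0.27² gives 7%, against 0.06² = 0.4% with the mean. At SD 8, 0.57² gives about 33%, against 0.21² or about 4% with the mean.

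**The case against.** **A reader might infer that the rule hides a rise in BP on treatment.** The documents do not support this. Vital signs are analysed as changes and compared between groups (Protocol Section 9.1.4, SAP Section 4.1.5), and the rule is the same at every visit and in both groups, so the understatement cancels. Step 4 shows that recorded rises become slightly more frequent. Only a cut on absolute level would miss high values, and neither document defines one for BP in the safety analysis. This objection stands in full.

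**A reader might also take 27–57% as the chance of admitting a patient above the entry limit.** That is a one-limb figure and leaves out the two-limb measurement at Visit 1. It also applies to a true systolic of 184, just over the limit. Such patients should be rare in this population ("Men and women at the age of 18 to 45 years old, inclusively"). Criterion 23 also rests on the Investigator's opinion, and the Investigator sees every reading. The entry effect is therefore secondary.

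**The size is assumed.** At SD 2 to 3 the average bias is under 1 mm Hg. The variance ratio concerns within-visit error only: with an assumed between-patient SD of 12 mm Hg, the total variance of BP levels rises by only 4–13% at SD 4 to 8. This is fair, but in a change analysis the stable between-patient part drops out, so the within-visit noise matters more there.

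**No trial conclusion depends on BP.** It is not an efficacy endpoint, and SAP Section 4 rests the efficacy claim on the primary parameter alone. This also stands, and it sets the priority of the point.

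**The cited recommendations may prescribe the rule.** Section 4.2.3.2.2 refers to national measurement recommendations that are not reproduced in the documents, so the fix has to be checked against them.

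One counter-argument does not stand. Using the limb with higher values at later visits does not correct the choice of the lowest repeat on that limb.

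**Conclusion.** The point holds as a minor measurement defect. The written rule understates BP by 3.2–7.9 mm Hg on average whenever a third reading is taken, and by 0.2–5.2 mm Hg over all measurements on one limb. It raises within-visit variance to 1.4–1.9 times that of the mean. The value to record when readings agree is undefined. The direction follows from taking a minimum. The sizes rest on the assumed SD of 2–8 mm Hg, independent readings, and the mean of two in the untriggered case.

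The between-group difference and the mean change are not biased, provided reading variability is alike across groups and visits; nothing in the documents suggests otherwise. The harm is to absolute levels and to precision, including more chance changes. For a true systolic of 184 on both limbs with the higher limb counted, the chance of a recorded value at or below 180 is 7–33% at SD 4–8, against 0.4–4% with the mean. Few patients are likely to be in that position.

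**What to change.** Replace the recording sentence in Protocol Section 4.2.3.2.2 with one that covers both cases: enter all readings in the eCRF, and use for analysis the mean of the two readings, or of the three when a third is taken, at every visit. State the same derivation in SAP Section 4.1.5. The 180/115 limit stays as it is.

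The cost is one sentence in each document and a few extra eCRF fields. No further measurements are needed. Recorded levels will be slightly higher than under the present rule, so the change should be in place before the first patient or applied to all patients from the stored readings. The sponsor should first confirm the wording against the measurement recommendations that the section cites.

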#### 4.2.3.2.3 Fill-in of TSS questionnaire

TSS, a questionnaire (point scale) for healthcare professionals, is used in clinical practice as well as clinical trials to evaluate dynamic changes of symptoms severity of the infection-inflammatory process in the throat (Bereznoy VV, Riley DS, Wassmer G, Heger M. Efficacy of extract of Pelargonium sidoides in children with acute non-group A beta-hemolytic streptococcus tonsillopharyngitis: a randomized, double-blind, placebo-controlled trial). One of such clinical trials with TSS questionnaire was conducted in 2005 in Germany, ©CRO Applertee AG. A version of TSS ©CRO Applertee AG was adapted for this protocol.

TSS (Tonsillopharyngitis Severity Score) is a questionnaire for evaluation of the following symptoms severity: pharyngalgia, difficulty in swallowing, salivation, hyperemia of pharyngeal mucosa, and body temperature increase according to a 4-point scale:

- 0 = no symptom;
- 1 = insignificant symptom;
- 2 = moderate symptom;
- 3 = significant symptom.

The axillary body temperature increase is rated as follows:

- 0 points: <37.5 °C;
- 1 point: 37.5 to <38.5 °C;
- 2 points: 38.5 to <39.5 °C;
- 3 points: >39.5 °C.

TSS is filled in by the Investigator based on the patient complaints and physical examination data. The Investigator summarizes the points obtained for every symptom to obtain a total sum of TSS points. A total sum of TSS points will be used at screening to evaluate for a subject's eligibility and baseline evaluation; at Visit 2 (Day 4), to measure efficacy of the trial therapy in the both groups; to evaluate the disease outcomes on Visit 2 (Day 4) and/or Visit 3 (Day 5), where applicable.

# 4.2.3.2.4 Evaluation of the throat pain intensity according to VAS

The patient will fill in the VAS to evaluate for the throat pain intensity at every visit to the trial site (Visit 1, Visit 2, and Visit 3 (where applicable)). Calibrated scales 100 mm in length with the relevant measuring instruments will be provided for the clinical trial.

The patients should evaluate their pain severity according to VAS at every visit (if possible, before administration of the painkillers (if those are required) or the study drug/comparator drug). The scale is provided in Appendix 5 to this protocol.

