#### Lidocaine

#### Absorption

Lidocaine absorption varies depending on the site and the method of administration. It is rapidly absorbed from the gastrointestinal tract, mucous membranes and through broken skin; however, before entering the systemic circulation it is mostly decomposed. The absorption from mucous membranes after topical application depends on the circulation and the total dose. After 30 minutes, less than 17% of the dose taken is present in the stomach and the intestines in the unchanged form, while less than 1.5% is present in other tissues.

The anesthetic action of lidocaine after topical administration emerges after two to five minutes and lasts for 30 to 45 minutes. The anesthetic effect is limited to the surface and does not extend to the submucosal structures.

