#### Secondary outcome measures

The secondary outcome measures in the both therapy groups were:

- The frequency of ≥50% total score reduction according to the TSS questionnaire completed by the Investigator as compared to the baseline in both Angal and ANTI-ANGIN® FORMULA groups at Visit 2 (Day 4).
- Total score reduction according to the TSS questionnaire, as well as a reduction in the symptoms (sore throat, difficulty in swallowing, salivation, erythema, and fever) after a 3-day therapy, at Visit 2 (Day 4), as compared to the baseline total score.
- A period of time required for disease symptoms relief, determined according to the patient's diary (subjective patient's evaluation), but no more than 5 days during the trial—for patients who have achieved the corresponding outcome.
- A proportion (%) of patients who fully recovered by Day 4 in Group A and by Day 5 in Group B (the outcome of a disease according to the objective evaluation by the Investigator, the total score according to the TSS questionnaire ≤2).
- A change in the sore throat intensity by 100 mm VAS (visual analogue scale filled in by the patient) at the beginning, after 3 days of therapy, and at the end of treatment in both groups.

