#### 7.2 Methods and timing for evaluation, recording, and analysis of efficacy parameters

The methods for efficacy criteria evaluation are described in Section 4.2.3.2. The first endpoint is evaluated in the morning at Visit 2 (Day 4, after 3 days of the trial therapy) before the study drugs intake. Other efficacy endpoints are evaluated in terms stated in Section 7.1.

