# 16.2 Appendix 2. TSS (Tonsillopharyngitis Severity Score) questionnaire

TE_004_ANG_LOZ		TONSILLOPHARYNGITIS SEVERITY SCORE (TSS)				PATIENT	PATIENT	
Visit*	Evaluation point	Discomfort severity*	SORE THROAT	DIFFICULTY IN SWALLOWING	SALIVATION	PHARYNGEAL MUCOSA HYPEREMIA	BODY TEMPERATURE INCREASE**	
VISIT 1	BASELINE	no symptom						
		insignificant symptom						
		moderate symptom						
		significant symptom						
VISIT 2	AFTER 3 DAYS OF	no symptom						
	THERAPY	insignificant symptom						
	evaluation before the first	moderate symptom						
intake of the study drug on Day 4	significant symptom							
VISIT 2/3	DISEASE OUTCOME*	no symptom						
		insignificant symptom						
		moderate symptom						
		significant symptom						
* To be filled in by the investi	gator at a Visit. Disease outcome applicat	ole if TSS>2 after 3 days of therapy						
Answers rate in points 0 = no symptom; 1 = insignificant symptom; 2 = moderate symptom; 3 = significant symptom.				** The axillary body temper: 0 = <37.5 °C 1 = 37.5 to <38.5 °C 2 = 38.5 to <39.5 °C 3 = ≥ 39.5 °C	ature increase is rated as follows:			
Investigator (Full name/Sig	nature)		1		Date			

Version 1.0 of September 2, 2016 in Russian, compiled based on the final version of November 21, 2005 in German. ® AodSUgg. AC

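### The pre-dose rating rule covers the Day 4 TSS row but not VAS at Visits 2 and 3 or the disease-outcome TSS, so these two secondary ratings may be made under local anaesthesia

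*Protocol*

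**What the plan says.** **Primary rating.** Protocol 7.2 states that the "first endpoint is evaluated in the morning at Visit 2 (Day 4, after 3 days of the trial therapy) before the study drugs intake". The TSS form (Appendix 2) carries the same condition on its row for the rating after 3 days of therapy, which must precede the first "intake of the study drug on Day 4". That row covers all five TSS items.

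**Everything else.** The next sentence of 7.2 reads "Other efficacy endpoints are evaluated in terms stated in Section 7.1". Section 7.1 gives days and visits, but no timing relative to a dose.

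**VAS.** Protocol 4.2.3.2.4 says "The patients should evaluate their pain severity according to VAS at every visit (if possible, before administration of the painkillers", and the sentence goes on to include the study and comparator drugs. SAP 2.2 has the same wording. The endpoint is the change in VAS "at the beginning, after 3 days of therapy, and at the end of treatment in both groups", compared between arms by t-test (protocol 9.1.3, SAP 4.1.3).

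**Disease outcome.** The third row of the TSS form, for Visit 2/3, applies "if TSS>2 after 3 days of therapy". It has no dose condition and is not limited to one arm. It serves the endpoint "A proportion (%) of patients who fully recovered by Day 4 in Group A and by Day 5 in Group B", defined as total TSS of 2 or less and compared by Fisher's exact test.

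**Drug action.** In protocol 2.1.1, lidocaine's effect "emerges after two to five minutes and lasts for 30 to 45 minutes". In 2.1.2, tetracaine acts within 1 to 2 minutes, with no duration given.

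**The concern.** The protocol has accepted that a throat-pain rating should be taken off drug, and says so for the Day 4 row. The same reasoning applies to a pain VAS and to a TSS total that decides whether a patient counts as recovered, yet the first has a conditional rule and the second has none.

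Baseline is drug-free in practice, because the Visit 1 list (4.2.4.1) places VAS and TSS before randomization and the first dose. A later rating made soon after a lozenge would mix transient numbness with resolution of disease in the change from baseline. For recovery, one point is enough: a total of 3 that reads as 2 after a lozenge becomes a recovery.

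Exposure is unlikely to be random. Protocol 6.3 says both drugs are taken as needed for a sore throat, so patients still in pain on a visit morning are the likeliest to have just used a lozenge. The trial is open-label.

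**Working it through.** The plan states no figure on this point, so the check compares the passages and adds one calculation for scale.

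**1. Timing rule by rating**

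| Rating | Dose-timing rule | Source |
|---|---|---|
| Baseline VAS and TSS | Before first dose by order of procedures | Protocol 4.2.4.1 |
| Day 4 sore-throat item (primary) | Mandatory pre-dose | Protocol 7.2, Appendix 2 |
| Other Day 4 TSS items and total | Mandatory pre-dose on the form | Appendix 2 |
| VAS, Visits 2 and 3 | Pre-dose only where possible | Protocol 4.2.3.2.4, SAP 2.2 |
| Disease-outcome TSS, Visit 2/3 | None | Appendix 2, protocol 7.1 and 7.2 |

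The 50% response endpoint, the score-reduction endpoints and recovery already reached on Day 4 all come from the protected row. The gap is the last two lines.

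**2. Does another rule close the gap?**
- Visits 2 and 3 require a fasted patient who brings the unused drug (4.2.4.2, 4.2.4.3). Section 4.2.3.2.6 defines fasting by the last meal, so it does not exclude a lozenge.
- The Visit 2 and Visit 3 procedure lists in those sections name neither VAS nor TSS, although Table 1 schedules both. No order of procedures protects them.
- The diary instructions (Appendix 3) give the lozenge interval and the daily limits but no rating-timing rule.
- The SAP text has no pre-dose rule for any TSS rating.

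**3. Which arm is exposed?**
- VAS at Visit 2: both arms.
- VAS and disease-outcome TSS at Visit 3: Group B only, for patients above 2 on Day 4.
- Disease-outcome TSS at Visit 2: as the form is worded, a Group A patient above 2 could be rated a second time that day. Group A returns unused drug at Visit 2, which limits the chance of a lozenge in between.

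**4. Scale**

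Inputs: lidocaine effect of 30 to 45 minutes (protocol 2.1.1) and a minimum interval of 120 minutes (protocol 4.4.4; section 6.1 does not repeat the interval for Angal).

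Share of the shortest interval under effect = duration / interval:
- 30 / 120 = 25%
- 45 / 120 = 37.5%

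This is the chance that a rating falls under lidocaine if it is made at a random moment during dosing at the shortest interval. It is an upper illustration, because use is as needed. No matching figure can be given for Group B without an assumed tetracaine duration.

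**The case against.** The strongest case against is that little of importance is left unprotected. The primary endpoint is pre-dose by explicit rule, and so are all five Day 4 TSS items. SAP section 4 rests the non-inferiority conclusion on the primary parameter alone and treats secondary variables as being of research interest. Visits are fasted, and the documents permit a post-dose rating without showing that one will occur. All of this stands, and it limits the point to two secondary ratings.

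A reader might infer more, in four ways that the documents do not support.

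- **That the primary endpoint is compromised.** This would need patients and sites to breach a written rule. The diary does not repeat the rule, but the consent pages are not available, so its absence is shown for the diary only.
- **That the gap favours Angal because its daily maximum is 10 against 6.** At Visit 3 only Group B is rated, so an untimed rating there could flatter only the comparator.
- **That Angal patients are 1.5 times as likely to be rated while numb.** Over 16 waking hours, nine lozenges at 2-hour spacing against six gives 9 / 6 = 1.5. The ninth falls at hour 16 and adds no waking coverage; eight give 8 / 6 = 1.33. Even that assumes dosing to the cap, ratings at random times of day and equal duration for both drugs. The primary rating and the blood draws are in the morning, when the daily maximum hardly matters.
- **That pre-dose status cannot be checked.** The TSS form shows a date but no time. The diary, however, records the time of each lozenge and the VAS form records its own time, so a rough check is possible.

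**Conclusion.** The point holds for VAS at Visits 2 and 3 and for the disease-outcome TSS row. The plan allows both to be made under active local anaesthesia, although it forbids this for the Day 4 TSS row. Where lozenges are taken at the 2-hour minimum, 25 to 37.5% of the interval lies within lidocaine's stated effect. That range assumes a random rating moment and applies to Angal only.

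Exposure can differ between arms, because Visit 3 exists only for Group B and the form leaves open a second same-day TSS for an unrecovered Group A patient. Neither the direction nor the size of any bias is established. The primary endpoint and the other Day 4 TSS endpoints are not affected under the written rules. Priority is low to moderate: the ratings do not decide non-inferiority, but they feed between-arm comparisons and the correction is cheap.

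**What to change.** 1. In protocol 4.2.3.2.4 and SAP 2.2, replace the conditional wording with the assessment rule used for the primary rating, for VAS at Visits 2 and 3.
2. In protocol 7.2 and Appendix 2, apply the same rule to the disease-outcome row. State that for Group A the outcome is taken from the pre-dose Day 4 row, with no second rating.
3. Add the rating time and the time of the last lozenge to the TSS form, and repeat the assessment-timing rule in the diary.
4. In SAP 4.1.3, report by arm the number of VAS and disease-outcome ratings made within 45 minutes of a lozenge, using diary times. Add a supportive analysis that does not replace the main one. Note that leaving out such ratings conditions on as-needed use after randomization and can itself introduce selection bias.
5. Reconcile protocol 4.2.3.2.4, which allows for painkillers, with 6.2.2, which prohibits them.

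Items 1 to 4 concern when ratings are made and recorded; they change no dose or treatment rule. The cost is wording in two protocol sections, two appendices and the SAP, two form fields and one table. The downside is that some ratings will be flagged as not pre-dose.
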